9.2 Assessments of outcomes

ICH: Specification of the efficacy parameters. Specification of safety parameters.

This section includes a description of each endpoint, what variables will be assessed/observed and how it will be done, including any related processes to promote data quality. In general, the standard measurement equipment gets calibrated by certified specialists sent out by the appropriate company to Sonova AG once per year. Study specific adjustments of the measurement tools get calibrated by the responsible study team member. Prior to study start, the PI uniformly trains the study team according to the study protocol, which is documented in a training log. Every measurement method used in this study is conducted according to its instruction. In this way, potential damages of a participants ears caused by unexpected loud sound levels are eliminated. Prior to every measurement, the participants absolve a training session to minimize a bias induced by training or learning effects. These data are not part of the analysis.

9.2.1 Assessment of primary outcome

ICH: Methods and timing for assessing, recording, and analysing of efficacy & safety parameters.

Procedure: After a successful screening as described in section 7.2, the data serving as primary outcomes are collected in a series of appointments lasting 1.5 to 2 hours each for the lab trials and one week for the home trials taking place between the lab trial appointments. The subjective and objective measurements that are applied to grant zero-defect overall performance of the new Phonak Hearing Systems regarding technical stability, audiological performance and handling are listed in section section 5.1. The general procedure of a lab trial can be described in a flow chart as follows:

[figure not shown]

Figure 6: Schematic procedure of a lab trial.

Testing takes place in one of the three double-walled sound-attenuating booths (Validation Room 1, 2 and 3). Participants are tested individually. All of them comfortably sit on a chair in the middle of the room and are consistently instructed what their task is both written in terms of standardized instructions and verbally to ensure that the task is understood. Then, stimuli (speech: words, numbers or sentences in quiet or in a specific background noise, also music or sound simulations, like an in car situation, in a cafeteria or in a reverberated room) are presented with a computer and loudspeakers of a number and of a defined arrangement according to the test method used, see figures 7 and 8. In case of a closed-set speech test, the participant are instructed to choose an answer on a touch screen. In case of an open-set task, the participant is asked to verbally repeat the things understood.

Instead of loudspeaker presentations also headphone presentations simulating hearing aids (single features or functions) as well as sound situations by pre-recorded sound files can be presented to the participant. The advantage is a highly controlled listening situation and a simple possibility to quickly switch between different hearing aids (or settings) in case of a paired comparison or a MUSHRA task which use subjective rating on a rating scales to evaluate different dimensions.

Measurement methods: The measurement method that comes into operation depends on the particular question that needs to be answered during an appointment. Most important aims for ensuring a high quality hearing system are both a maximum *speech understanding* in every listening situation and a good *sound quality*.

Speech understanding can be assessed by standardized speech tests both in quiet and in noise (see figure 7, 8 and section 5.1, table 4). To evaluate speech intelligibility in quiet, different normed speech tests are available, such as the Freiburger, GöSa and WAKO. These methods are complemented with a new methodology, the Phoneme Perception Test (PPT), a language independent test, assessing a participant's detection, distinction and recognition threshold for single fricatives (high frequent sounds like /s/, /sh/, /f/) which are mostly affected by a hearing loss. In addition to speech understanding in quiet, speech intelligibility in noisy surroundings needs to be evaluated. The OLSA method as well as the GöSa in noise, the WAKO in noise and the Acceptable Noise Level (ANL) test provide a basis. Another important topic is the localization capability of a hearing aid user to know from which direction a sound originates from. The Localization Test delivers appropriate results.

Sound quality is evaluated by using methods of subjective rating on a rating scale using the Paired Comparison method or the MUSHRA. Furthermore, sound quality can be rated using qualitative and quantitative questionnaires (p/eCRF) during both the home trials and the lab trials or by conducting structured interviews, unstructured interviews or group discussions where the data collected are of narrative character. In this way data can be supplemented by some information that could not be captured using the standardized test methodologies.

The Real-Ear Measurement (REM) tool is an objective methodology to measure the hearing instrument's frequency response under real ear conditions. A Real-Ear-Measurement includes the established real ear measurements of REUG (real ear unaided gain), REAG (real ear aided gain), REIG (real ear insertion gain) and RECD (real ear coupler difference). For the real ear measurement a soft silicone probe tube is thread through the custom product vent. The individual length of the probe tube is measured via otoscopy. The tip of the probe tube has to be placed in the residual ear canal volume of the participants ear. After the insertion of the custom product in the participants ear, the ear canal gets stimulated by an acoustic source from an exterior sound source. With the probe tube in the residual ear canal the frequency response is recorded.

Further tests used are the Categorical Loudness Scaling a psychoacoustic method to capture the individual subjective loudness perception, the TEN test to evaluate dead regions in the cochlear, cognitive measures to assess hearing fatigue and listening effort, occlusion measurements to investigate occlusion effects mainly occurring in ITE devices.

[figure not shown]

Figure 7: Measurement setup: Freiburger, WAKO and GöSa in quiet, PPT, Categorical Loudness Scaling. Both study participant and PI in sound-attenuating booth.

9.2.5 Assessments in participants who prematurely stop the study

Withdraw without Adverse Event: If a subject is withdrawn from the study without having an AE, an audiogram will be recorded in a final appointment and the outer ear will be controlled to ensure that there are no damages through the study.

Withdraw with Adverse Event: If a subject is withdrawn in case of an AE, a referral to an independent doctor will be carried out. In accordance with the subject and the doctor, an additional appointment will be arranged to record a status update.

9.3 Procedures at each visit

Each study part follows the same pattern:

- Screening
- Pre-study or main study
- Final appointment

This pattern ensures the best method to not unnecessarily extend the study and to not perform tests with participants, which are not needed. For that reason first a pre-study is conducted with only a few participants to proof the study concept and the scientific interrogation behind it. If the results of the pre-study are promising, the main study will start.

9.3.1 Screening appointment

- Mapping to an encoded and randomized subject ID
- Discussion of the subject information and signing of the informed consent which were sent in advance by post or email
- Recording of the subject's audiological history
- Ear and ear canal assessment (otoscopy)
- Hearing test (pure tone and speech audiometry)
- In case of tinnitus: Tinnitus Pitch and Loudness Matching
- Explanation of in-/exclusion criteria
- Decision if patient can participate in the trial regarding to the in-/exclusion criteria
- eCRF Screening
- eCRF Audiometry
- Scheduling of the next visit

9.3.2 Pre-study appointment

- Ear canal assessment
- Fitting of hearing instrument (randomized) and documentation in eCRF
- Measurements objective and subjective (randomized), see section 5.1 and 9.2.1
- Fine tuning hearing instrument, if necessary
- Introduction to handling of hearing system (randomized)
- Introduction to CRF
- Signing of the device delivery form
- Schedule next visit
- eCRF Adverse Event, if applicable

9.3.3 Main study appointments

A main study appointment will only be executed if the pre-study results were promising. The procedure for the main study appointments is the same as for the pre-study appointments (see section 9.2.1).

9.3.4 Final appointment

- Ear canal assessment

- Hearing test (pure tone)
- In case of tinnitus: Tinnitus Pitch and Loudness Matching and comparison with the outcome of the screening. If the intensity is increased, a referral to an independent doctor will be carried out. In accordance with the subject and the doctor, an additional appointment will be arranged to record a status update
- Calculation and signing of the compensation form
- Signing of the device return form
- Collecting all study material
- Hand out of study feedback form
- eCRF Adverse Event, if applicable

10. SAFETY

(ClinO Art. 37-43; ICH/E6 6.8; ISO14155 8.2.5, A.14; AGEK 4.1; SPIRIT # 22, 30)

Description of plans for collecting, documenting, assessing, reporting, and managing solicited and spontaneously reported adverse events and other unintended effects of trial interventions or trial conduct.

10.1 Drug studies

N/A

10.2 Medical Device Category C studies

N/A

10.3 Medical Device Category A studies

10.3.1 Definition and Assessment of safety related events

All hearing systems are CE-labelled, i.e. the safety of the user is granted. However, the hearing aid can reach a high maximum power output (MPO) which can be louder than the user's threshold of uncomfortable levels is. For this reason, the MPO will always be set accordingly to clinical expertise at a level so that no injuries can occur. Consequently, neither during the measurements nor in the daily routine the safety of the participants will be compromised.

In order to ensure that each MD works correctly, every device will be checked before each application by the appropriate investigator. Furthermore, the participant is instructed to take note of any unexpected incidences (e.g. redness or swelling of the outer ear) and to document these in the questionnaires (p/eCRF). Pressure points are also controlled by the investigator at the beginning and at the end of an appointment. In the case that wearing the test devices in the time between the appointments becomes uncomfortable or even painful, the subjects are instructed not to wear the devices anymore and to contact the investigator for information and, if necessary, a doctor.

Furthermore, the participants are advised not to wear the device if a setting is not acceptable or tolerable, but to contact the investigator for an additional appointment. If any unexpected incidences occur during the lab trials the participant will be encouraged to immediately report the issue to the investigator.

10.3.2 Reporting of Safety related events

Reporting to Sponsor: Health hazards that require measures are reported to the Sponsor within 24 hours upon becoming aware of the event. If any unexpected AEs are to occur (e.g. chronic pain in the ear canal after MD application), the event has to be documented in the AE eCRF. Depending on the event, a decision needs to be made whether the participation in the study has to be interrupted or

even cancelled. If required, a referral to an independent doctor is to be carried out. An additional appointment will be arranged with the test participant (e.g. after one to two weeks) in order to record and document the status update.

Reporting to authorities: In Category A studies it is the investigator's responsibility to report health hazards requiring measures to the local Ethics Committee within 2 days.

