Check In- /Exclusion Criteria	x											
Decision Subject Participation	x											
Subject Information and Informed Consent	x											
Encoded Subject ID	x											
eCRF Screening	x											
eCRF Audiometry	x											x
Randomisation	x											
Hearing System Fitting	x											
Objective and Subjective Measurements		x	x	x	x	x	x	x	x	x	x	(x)
eCRF Objective and Subjective Measurements		x	x	x	x	x	x	x	x	x	x	(x)
Introduction to Handling		x	x	x	x	x	x	x	x	x	x	
Scheduling Next Visit	x	x	x	x	x	x	x	x	x	x	x	
eCRF Final Appointment												x
Capture of Adverse Events and Device Deficiencies	x	x	x	x	x	x	x	x	x	x	x	x

Table 1b: Main study: N = max 30 (no pre-study subjects)

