3.7 Risks / Benefits

(ClinO, Appendix 4, 3.5; Art 25d2; ICH/E6 6.2.3; AGEK 11.1; SPIRIT #6a; MD: ISO 14155 Annex A & ISO 14971)

ICH: Summary of the known and potential risks and benefits, if any, to human subjects.

There are five known risks:

1. Infections can be caused by injuries of the ear canal which can occur by the placement of the acoustic coupling (e. g. receiver, earpiece) to the outer ear canal or by the placement of an ITE device. Therefore, the ear canal will be thoroughly checked and assessed during the study.
2. Pressure points can be caused by the hearing aid or the acoustic coupling. In case of pressure points, the hearing aid should not be worn until it healed up. The cause of the pressure point would then be investigated.
3. Tinnitus can be cause by wearing of the hearing aids. An existing tinnitus can be temporarily amplified. If the tinnitus doesn't improve after several days of not wearing the hearing aid, an assessment with an independent doctor (ENT) is necessary.
4. A headache can occur, especially for new hearing aid users. If a headache appears, the subject is instructed to interrupt the hearing aid use until the audiologist applies a new fitting (e.g. reduced gain level) to acclimatize the subject to the devices.
5. The hearing aid can reach a high maximum power output (MPO). The MPO will be set accordingly to clinical expertise at a level that no injuries can occur.

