5.3 Other Outcomes of Interest

Other outcomes of interest are side-effects.

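### Section 10.3.2 ties adverse event (AE) eCRF entry to unexpected events, while the schedules and visit procedures have no such limit, so foreseeable side effects could be recorded inconsistently

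*Combined protocol and SAP*

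**What the plan says.** Section 10.3.2 contains the one sentence in the available text that says which events must go into the AE eCRF: "If any unexpected AEs are to occur (e.g. chronic pain in the ear canal after MD application), the event has to be documented". It does not mention expected events.

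Section 10.3.1 uses the same restriction twice. For the questionnaires, "the participant is instructed to take note of any unexpected incidences". During lab trials, participants are encouraged to report unexpected incidents to the investigator at once.

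Other places carry no such limit. Tables 1a and 1b in the Study Schedule, repeated in Section 9.1, have a row headed "Capture of Adverse Events and Device Deficiencies" that is marked at every visit. Section 9.3.2 lists "eCRF Adverse Event, if applicable", and Section 9.3.4 has the same item for the final appointment. Section 9.3.3 extends the pre-study list to the main study: "The procedure for the main study appointments is the same as for the pre-study appointments". Section 12.1.2 lists AEs and SAEs as source data without a filter.

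Section 3.7 says "There are five known risks" and names ear canal injury with infection, pressure points, tinnitus, headache and high maximum power output. Section 5.3 says "Other outcomes of interest are side-effects".

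**The concern.** An effect that the protocol lists as a known risk is, in ordinary usage, expected. An investigator who takes Section 10.3.2 at its word could leave a headache or a pressure point off the AE eCRF and still comply. A colleague working from the visit checklist could enter the same event and also comply. Section 10.3.1 is headed as the place where safety-related events are defined, but it defines neither the event nor the qualifier.

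What is at stake is whether the side-effect data are complete and mean the same thing across participants, investigators and the successive studies run under this protocol. Long-term safety is an objective (Section 4.4). The AE eCRF is the only AE-specific form that the available text names, so an event left off it may not reach any count of side effects.

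**Working it through.** The documents state no side-effect rate, count or AE-based sample size, so there is no figure to reproduce. The check is a reconciliation of the text.

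**Step 1. Where AE recording is addressed, and whether the restriction applies.**

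| Place | What it governs | Limited to unexpected? |
|---|---|---|
| 10.3.2 | Which events must enter the AE eCRF | Yes |
| 10.3.1, questionnaires | What participants write down | Yes |
| 10.3.1, lab trials | What participants report at once | Yes |
| Table 1a (also 9.1) | AE capture, 4 of 4 visits | No |
| Table 1b (also 9.1) | AE capture, 12 of 12 visits | No |
| 9.3.2, carried to the main study by 9.3.3 | AE eCRF, if applicable | No |
| 9.3.4 | AE eCRF, if applicable | No |
| 12.1.2 | AEs and SAEs as source data | No |

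The unrestricted entries mostly say when to capture events or which form to use. Section 10.3.2 says which events qualify. Sections 9.3.2 and 9.3.4 leave applicability open, and the only stated criterion for it is in 10.3.2.

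**Step 2. How each known risk would reach the AE eCRF.** Of the five listed, high maximum power output is a device hazard and not itself a side effect, which leaves 5 − 1 = 4.

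- *Ear canal injury or infection:* the ear canal is examined at appointments. No text sends a positive finding to the AE eCRF.
- *Pressure points:* the investigator checks for them when an appointment opens and closes (10.3.1). No route to the form is stated.
- *Tinnitus:* matched at screening and compared at the final appointment where present (9.3.1, 9.3.4). An increase leads to referral; entry on the form is not mentioned.
- *Headache:* no structured check. Detection depends on the participant speaking up.

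Detection is therefore provided for in three of the four. A recording rule is stated explicitly for none of them.

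**Step 3. Size.** Let q be the share of side effects that are expected, and m the share of those not entered. Then

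fraction missed = q × m.

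- If the visit-level wording governs, m = 0 and the fraction is 0.
- If Section 10.3.2 is applied as exclusive, m = 1 and the fraction is q.

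The documents give neither q nor m, so the fraction lies between 0 and q and cannot be narrowed.

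**The case against.** Section 10.3.2 does not say that expected events are left out. The visit procedures name the AE eCRF without a filter, and the schedules mark AE capture throughout. The protocol's own examples also suggest a loose use of the word. Section 10.3.1 illustrates an unexpected incident with reddening and swelling of the outer ear, which overlaps the ear canal and pressure-point risks in 3.7; ear canal pain, the example in 10.3.2, is close to them too. Participants are separately told to contact the investigator if wearing becomes uncomfortable or painful, and a headache that leads to a new fitting would come to staff attention.

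Much of this stands, and it rules out several stronger readings:

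- A reader might infer that only unexpected events are recorded and that side effects will therefore be under-counted. Exclusivity is not in the text, so a loss is possible but not established.
- A reader might count five side effects outside the rule. The protocol lists five risks, and one is a device hazard.
- A reader might put a number on the missing participants. That needs an assumed event rate and total non-recording, and the documents support neither.
- A reader might infer bias between devices, since investigators are not described as blinded. However, the benchmark in 5.2 works from Table 4, which has no side-effect rate; 5.4 gives safety outcomes as not applicable; and no between-device comparison of AEs is stated.

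What the objection does not remove is the conflict. Finding an event is not the same as entering it, and examples that overlap the known risks show that the qualifier has no fixed meaning. The contents list names Sections 9.2.3 and 9.2.4, whose text is not in the available copy. A recording rule may stand there, but 10.3.1 and 10.3.2 would still have to agree with it.

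**Conclusion.** The point holds as an internal inconsistency in data capture that could make the recording of foreseeable side effects incomplete or uneven. It does not show that an under-count will occur. The conclusion rests on reading the known risks in 3.7 as expected events, and on 9.2.3 and 9.2.4 not already settling the matter. The first is the ordinary meaning but is not stated in the plan; the second cannot be checked here. Confidence is moderate. The correction is still worth making, because side-effects are a named outcome and the change costs very little.

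**What to change.** - In Section 10.3.2, delete the word unexpected from the documentation sentence, so that every AE, expected or not, is entered in the AE eCRF with the device worn at the time. The device is needed because in the cross-over design of Section 6.1 a participant wears more than one.
- In Section 10.3.1, delete the same word from both participant instructions, and define an AE and expectedness there.
- Keep expected or unexpected as a coded field on the form, so that the distinction remains available for analysis.
- Align the wording with Tables 1a and 1b, Sections 9.1 and 9.3.2 to 9.3.4, and Sections 9.2.3 and 9.2.4.

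This concerns recording only. The sentences on interruption, referral and reporting to the sponsor and ethics committee should keep their present scope; because some of them follow directly on the edited sentence, the revised text should make that clear. The cost is a few wording changes, one coded field, one device field if the form lacks it, and slightly more AE form entry.

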11. STATISTICAL METHODS

(ICH/E6 6.9; AGEK 8; SPIRIT # 14, 20)

Statistical considerations

ICH: A description of the statistical methods to be employed, including timing of any planned interim analysis(es).

This section describes the statistical considerations done for the study and the level of significance that will be used. The traceability of the study data is warranted for both the pre-study and the main study at any time. This means that an unauthorized and an accidentally change, deletion or copy of the gathered and analysed data is excluded. In case of a pre-study, the data are collected in a paper based manner. In case of the main study, the data are gathered both paper based and electronically whereat the paper based data are all fed into the clinical database eClinicalOS by the respective investigator as soon as possible and the source data verification is undertaken by the monitor (see section 12.1 for data handling details).

11.1 Hypothesis

This is a methodical evaluation in which new hardware and software technologies of Phonak products shall be compared with previous outstanding Phonak Hearing Systems and with equivalent competitor devices regarding a zero-defect overall performance and a maximum audiological benefit for the user. Hence, this study will not test a specific hypothesis.

11.2 Determination of Sample Size

ICH: The number of subjects planned to be enrolled. In multicentre trials, the numbers of enrolled subjects projected for each trial site should be specified. Reason for choice of sample size, including reflections on (or calculations of) the power of the trial and clinical justification.

Based on numerous publications in the field of audiology research using standardized measurement methods testing hearing impaired subjects as well as on Sonova AG's extensive study experience, a number of maximum 20 subjects per study is sufficient to obtain statistically significant results on a significance level of 5%.

In the case of the pre-study a maximum of 5 subjects is included, since merely the study concept needs to be proved, and no inferential but only descriptive statistics is carried out. Later, during the main study, both descriptive and inferential statistics are executed. In the past, typically 20 subjects participated per study leading to significant results approaching the primary objective (zero-defect overall performance of the new Phonak Hearing Systems). To tackle the secondary objective (product benchmark) a number up to 30 subjects have taken part in several previous investigations. This case is founded in the fact that a study design of parallel groups, either containing 10 or 15 subjects each, is applied as soon as more than one competitor device is compared to the Phonak Hearing System. For this reason, an appropriate number of subjects will be included during the planned investigations.

